4.1 Sample size

4.1.1 Sample size calculation (pre covid)

For the primary outcome ("Healthy baby"), in order to detect a difference in babies born "healthy" of 8% between the control and intervention arm, with 90% power and a 5% significance level, we would require at least 866 women per arm (i.e. 1732 total). This calculation also assumed an outcome proportion of 69% in the control arm, accounts for clustering within the intervention arm with an intra-cluster correlation (ICC) of 0.05 (in the intervention arm), mean group sizes of 8 with cluster size variability assuming Poisson distribution and assumes 10% drop-out in both arms. This sample size provides 84.8% power to detect a difference between arms of 7.3% in our, former primary outcome, spontaneous vaginal birth. Thus, a sample size 1732 is sufficiently powered to detect changes in both the primary outcome and SVD (now a secondary outcome).

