5.5 General analysis principles

The analysis of primary, secondary, and, where possible, additional outcomes will be adjusted for the stratification factors which were used during randomisation, centre, and ability to speak English, only. All main analyses will be performed on a complete case basis (ignoring missing data) for the outcomes in question. A missing category will be created for the only covariate in the models "ability to speak English". The significance for statistical tests (alpha) will be 5%, all confidence intervals will be presented at the 95% level and all p-values will be two-sided. As the intervention arm includes group pregnancy circles, clustering will be accounted for in the intervention arm using pregnancy

circles as the units of clustering, while participants in the control arm will be modelled as a cluster size of one [1].

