5.9 Analysis of primary, secondary and additional outcomes

The following table shows the variable type of outcomes in this study:

		•
	Outcomes:	
Binary	Continuous	Categorical
-healthy baby composite	-attendance at antenatal care	-continuity of care
-spontaneous vaginal delivery	-women's empowerment	-Caesarean delivery
-breast feeding initiation	-social support	-place of birth
-breastfeeding continuation	-self efficacy	- additional measures of
-postnatal depression	-prenatal stress	satisfaction
-live baby	-health literacy	- choice and involvement in
-born at term	-mental wellbeing	care
-appropriate weight for	-postnatal symptoms	- preparedness for labour
gestational age	-satisfaction with care	- confidence in caring for baby
-not admitted to a neonatal	-Infant birth weight in grams	- immunisation
care unit		

Main analysis model (binary outcome)

The primary outcome data for the 'Healthy Baby' composite will be extracted via a postpartum maternity records audit and be analysed using a nested multilevel logistic mixed effects model with two random intercepts estimating a cluster and site-specific effects in both arms (1). Although site is a stratification factor, it has been included as a random effect due to the high number of sites included. In the intervention arm, within Pregnancy Circle cluster correlation will be accounted for and in the control arm each participant will be modelled as a cluster of size 1. The other stratification factor used in this trial is the ability to speak English and will be included as a fixed effect covariate. The resulting model will produce an odds ratio for the odds of giving birth to a 'healthy baby' in the intervention versus the control arm. The outcome will be assessed at the participant's level (mother) following this rule: if a mother has multiple births for the same delivery (e.g. twins), the 'Healthy Baby' composite will be equal to 'yes' only if all babies are healthy. Otherwise, Healthy baby will be equal to 'no'.

Specifically, let y be the binary outcome, i is the individual participant indicator (mother), j is the pregnancy circle indicator, t is the intervention indicator (0 = control, 1 = intervention), θ is the intervention effect, θ_0 is an intercept term, I is the site indicator, and θ_{ki} represents further covariates (ability to speak English in this instance). Then,

$$Logit[Pr(y_{iil}=1)] = \beta_0 + \theta t_i + \beta_{ki} + v_l + u_i$$

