Primary outcome is in bold and underlined and secondary outcomes are in bold and italic

^{*} PC for Pregnancy Circle group

^{**} ICC for clustering in intervention group (cluster is PC group)

^{***} Confidence interval is established using Swiger's method

Table 3: Results of secondary and additional continuous outcomes at 35 weeks and 3 months post-partum

	Number in	cluded in	Summary	measure	Treatment	effect		
	analy	/sis	-					
Outcome	Usual care	PC	Usual care	PC	Mean	(95% CI)	p-value	ICC**
	n (%)	n (%)	Mean (SD)	Mean (SD)	difference			[95 % CI]***
Pregnancy-								
related								
Empowerment								
Scale (PRES)								
Range 16-64								
Week 35								
Friends and								
family test								
Range 1-5								
Week 35								
Month 3 pp								
Emotional								
Wellbeing								
(SWEMWBS)Ra								
nge 7-35								
Week 35								
The Duke-UNC								
Functional								
Social Support								
Questionnaire								
Range 8-40								
Month 3 pp								
Pearlin								
Mastery Scale								
Range 7-28								
Month 3 pp								
Revised								
prenatal								
distress scale								
Range 0-16								
Week 35								
Infant birth								
weight (g)								
Month 3 pp								
Health literacy								
Range 1-20								
Week 35								

Post natal				
symptoms				
(NPEU)				
Range 0-5				
Month 3 pp				
Number of				
antenatal care				
sessions				
attended				

Secondary outcomes are in bold and italic

Table 4: Analysis of categorical Additional Outcomes

	Number include	ed in analysis	Summary	measure	
Outcome	Usual care n (%)	PC n (%)	Usual care %	PC %	P value for between group difference
How do you feel about the care you received					
from midwives? (week 35)					
very happy					
fairly happy					
not very happy					
very unhappy					
Missing					
How do you feel about the care you received					
from midwives (before the birth of your					
baby)? (3 months pp)					
very happy					
fairly happy					
not very happy					
very unhappy					
Missing					
Caesarean delivery					
Planned					
Emergency					
None					
Missing					
Place of birth					
Hospital obstetric unit					
Hospital alongside midwifery unit					
Freestanding midwifery unit					
Home					
Other					
Missing					

^{*}PC is for Pregnancy Circle group

^{**} ICC for clustering in intervention group (cluster is PC group)

^{***} Confidence interval is established using Swiger's method

Has your new baby had their routine		
immunisations?		
Yes 2 months		
No 2 months		
Yes 3 months		

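### Swiger's interval is too narrow for the circle ICC of binary outcomes close to 100% in Table 2, and the SAP does not say which ICC is printed

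*SAP*

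**What the plan says.** Table 2 in SAP 8.4 is the results shell for nine binary outcomes, from healthy baby and baby alive to postnatal depression. Its last column is an ICC with a 95% interval. The footnotes describe the ICC as "ICC for clustering in intervention group (cluster is PC group") and fix the interval: "Confidence interval is established using Swiger's method". Table 12 (healthy baby under the opposite rule for multiple births) and Table 3 (continuous outcomes) carry the same two footnotes.

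Section 5.9 analyses binary outcomes with a "nested multilevel logistic mixed effects model with two random intercepts", one for circle and one for site. Section 5.5 adds that "all confidence intervals will be presented at the 95% level and all p-values will be two-sided". Section 4.1.1 planned the trial on an "intra-cluster correlation (ICC) of 0.05" in the intervention arm and "assumed an outcome proportion of 69% in the control arm".

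The SAP does not say whether the printed ICC of a binary outcome is a one-way ANOVA ICC of the 0/1 data (proportion scale) or the ICC implied by the logistic model (latent, log-odds scale).

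**The concern.** Swiger's method takes the large-sample variance of the one-way ANOVA ICC for normally distributed data and adds and subtracts 1.96 standard errors. Its inputs are the estimated ICC, the number of groups and the group size. The event rate is not among them. A binary outcome near 0% or 100% has few informative events, so the ICC estimate varies more than the formula allows.

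The open question of estimator and scale adds to this:

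- **ANOVA ICC.** The formula at least belongs to the estimator, but its normal-theory variance can fail for rare events. A one-way ANOVA also has no site term, so between-site variation that the model in 5.9 separates would enter the circle ICC. The size of that effect was not quantified.
- **Model ICC.** Swiger's variance is not the variance of a latent-scale ICC. A latent ICC also cannot be compared directly with the planned 0.05.

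At stake is the accuracy of the published error bars on the circle ICCs. No test or treatment estimate depends on them.

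**Working it through.** **Inputs from the SAP.** Healthy baby: 69% in controls, so 69 + 8 = 77% with circles; ICC 0.05; mean circle size 8 with Poisson variation; 10% drop-out (4.1.1). Circles in the primary population: 45 completed and 33 with a high or moderate dose (8.3), plus 566 / 2 / 8 = about 35 after the pause (4.1.2), so about 113.

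**Assumed.** The SAP gives no rate for live baby or the other components; 93%, 98% and 99% 'yes' are used. The background stillbirth figures in 8.1 (3.22 per 1000 for White women and 7.23 per 1000 for Black women) place live baby near 100%, before earlier losses and neonatal deaths are counted. Drop-out is ignored in the simulation.

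**The plan's own figure.** The SAP states no width or coverage for the ICC interval. Its sample size checks how the clustering inputs are read. The unclustered size is 646 per arm. The design effect is 1 + ((1 + 1/8) x 8 - 1) x 0.05 = 1.40, in the intervention arm only. Then 646 x (1 + 1.40)/2 / 0.9 = 861 per arm (855 with a pooled variance), against 866 stated. The inputs are read as intended.

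**Swiger's standard error.**

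SE = sqrt{ 2(N-1)(1-r)^2 [1+(n0-1)r]^2 / [n0^2 (N-k)(k-1)] }

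With k = 113, N = 113 x 8 = 904 and n0 = about 7.99:

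- r = 0.05: sqrt(2 x 903 x 0.9025 x 1.821 / (63.8 x 791 x 112)) = 0.023
- r = 0.01: sqrt(2 x 903 x 0.9801 x 1.145 / (63.8 x 791 x 112)) = 0.019

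The same values apply at every event rate. Yet 904 women give about 208 'no' outcomes at 77%, 18 at 98% and 9 at 99%.

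**Coverage around an ANOVA ICC** (113 circles, Poisson mean 8, logit-normal circle effects, 3000 runs per row):

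| Rate 'yes' | True ICC | Mean Swiger SE | Actual SD | Coverage of nominal 95% |
|---|---|---|---|---|
| 69% | 0.01 | 0.0189 | 0.0190 | 94% |
| 69% | 0.05 | 0.0228 | 0.0233 | 94% |
| 77% | 0.01 | 0.0189 | 0.0190 | 94% |
| 77% | 0.05 | 0.0228 | 0.0242 | 93% |
| 93% | 0.01 | 0.0189 | 0.0212 | 92% |
| 93% | 0.05 | 0.0227 | 0.0321 | 84% |
| 98% | 0.01 | 0.0188 | 0.0263 | 85% |
| 98% | 0.05 | 0.0223 | 0.0498 | 62% |
| 99% | 0.01 | 0.0186 | 0.0321 | 77% |
| 99% | 0.05 | 0.0216 | 0.0644 | 50% |

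A repeat that adds ICC 0 and 0.02 gives, for ICC 0, 0.01, 0.02 and 0.05, coverage of 90%, 85%, 79% and 64% at a 98% rate, and 86%, 76%, 68% and 49% at 99%. The two sets agree to within about two percentage points. With 100 to 125 circles and with beta-binomial data as well, coverage at ICC 0.05 is 62-70% (98%) and 50-59% (99%). For healthy baby it stays at 92-95% for ICCs from 0 to 0.10. With normal data it is 94-95%.

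**If Swiger's SE is attached to the latent ICC**, variance / (variance + pi^2/3), with 200 runs per setting: at a proportion-scale ICC of 0.05, coverage is 84.5% (69% rate), 80.5% (77%), 29% (98%) and 26% (99%). At 0.01 it is 97-98% for healthy baby. At a 77% rate, a proportion-scale ICC of 0.05 corresponds to a latent ICC of 0.084.

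**The case against.** **The primary outcome is largely untouched.** A reader might infer that every binary interval in Tables 2 and 12 is too narrow. The figures do not support that. On the ANOVA reading, healthy baby covers 92-95%, so Table 12 has no material error. The lower coverage for healthy baby needs Swiger's SE to be paired with the latent ICC, a pairing that the SAP does not state. Naming Swiger's method points, if anything, to an ANOVA ICC. This stands: the text shows an unstated estimator, not a wrong pairing.

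**Strong clustering of live baby is implausible.** At a 98% rate, a proportion-scale ICC of 0.05 is a latent ICC of 0.322. The circle variance is then 0.322/0.678 x 3.29 = 1.56 (SD 1.25), so one SD multiplies the odds by about 3.5. Nothing in the SAP supports that for pregnancy loss or death, and the planned 0.05 is for healthy baby. This also stands. The relevant range for live baby is probably ICC 0 to 0.01, where coverage is still only 85-90% at 98% and 76-86% at 99%.

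**Negative lower limits prove nothing here.** Many intervals will fall below zero, which might be read as a further fault of using the method on binary data. But the share is the same with normal data: 39% (normal) against 41% (binary at 77%) at ICC 0.05, and 88% for both at 0.02. It reflects limited information, not an interval that is too narrow.

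**The column is descriptive.** The odds ratio, risk difference, bootstrap intervals and p-values do not use it, and no section plans a formal check of the assumed 0.05. This stands and limits the severity.

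**Conclusion.** The point holds for the rows of Table 2 whose outcome lies close to 100%. Live baby is the clear case; other rows qualify only by assumption about their rates. There a nominal 95% interval covers about 85-90% (98% rate) or 76-86% (99% rate) at ICCs of 0 to 0.01, and about 64% or 49% at 0.05. For healthy baby, Table 12 included, coverage is near nominal if an ANOVA ICC is printed. It falls to about 80-85% only on the latent-ICC reading and at a proportion-scale ICC of about 0.05. The SAP leaves that reading open.

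The conclusion rests on the assumed component rates, on about 113 circles (100 and 125 give similar results) and on simulation without site effects or drop-out. It should not be read as a doubt about the trial's main result: the treatment effect, its interval and its p-value are unaffected. Severity: minor.

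**What to change.** Change the ICC footnotes to Tables 2 and 12:

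- State the estimator and scale of the ICC for binary outcomes.
- Replace Swiger's method with a 95% profile-likelihood interval for the circle variance from the logistic mixed model in 5.9, converted to an ICC. Also give the proportion-scale value, which can be compared with the planned 0.05.
- Where the circle variance is estimated at zero, report the upper limit only. Where the convergence sequence in 5.9 removes the circle effect, state that the ICC is not estimable. A zero estimate will not be unusual: at a 98% rate it occurred in 17-34% of simulated trials at ICCs of 0.01 to 0.05.
- Keep Swiger's method for Table 3.

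In the same kind of simulation, profile-likelihood intervals covered 93-99% (300 runs per setting). This was checked with a circle effect only, not with circle and site together. A percentile cluster bootstrap of the ANOVA ICC is not a good substitute: it covered only 73-88% at rates of 98-99%.

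The cost is a revised footnote, a little more code and wider intervals.

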5.14 Dose response analysis

We will explore the dose-response relationship between the number of sessions attended and the primary outcome in the intervention arm. The scale of this attendance variable is 0-8 where 0 = no antenatal circles attended and 8 = 8 antenatal circles attended. Dose will be used as a continuous variable assessed in a model fitted on intervention group participants only.

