5.16.6 Sensitivity analysis of the dose-response relationship

In this analysis, we will change the assumptions regarding missing data in two steps: 1) we will consider that women attended all sessions where there is a missing value 2) we will impute the median and then mean value for women where the number of session(s) is missing.

6. Other analyses, data summaries, and graphs

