Outcome	Usual care n (%)	PC* n (%)	Usual care % of yes	PC* % of yes	Odds ratio [95% CI]	Risk diff. [95% CI]	p-value	ICC** [95 % CI]***
Healthy baby								

^{*} PC for Pregnancy Circle group

Table 13. Sensitivity analysis investigating the robustness of CACE analysis* results to the exclusion restriction assumption (that the treatment effect is zero for non-compliers)

	OR (95%CI)	RD (95%CI)	P-value
Main analysis			
Sensitivity analysis			

^{*}effect of intervention amongst 'compliers' when exclusion criterion does/does not apply

Table 14. Sensitivity analysis: Results of analysis accounting for the COVID-19 pandemic

Pandemic phase	Number analysed N*	OR (95%CI)	RD (95%CI)	P-value
Pre-pandemic				
No dose				
Low/very low dose				
Medium/high dose				
Post-pandemic				
Pooled, aggregate effect				

^{*}Primary outcome is in bold and underlined

^{**} ICC for clustering in intervention group (cluster is PC group)

^{***} Confidence interval is established using Swiger's method

Table 15. Sensitivity analysis: Results of dose-response relationship between primary outcome and number of antenatal care sessions attended with different missing data assumptions

Missing data assumption	Number included in analysis (N)	Regression coefficient (β)	95%CI	P-val	ue
N of antenatal					
care session(s)					
(original					
assumption)					
N of antenatal					
care session(s)					
(mean					
imputation)					
N of antenatal					
care session(s)					
(median					
imputation)					
N of antenatal					
care session(s)					
(attendance					
imputation)					

Table 16 Sensitivity analysis for protocol deviations

Protocol deviation	ana	nber lysed (%)	OR (95%CI)	RD (95%CI)	P-value
	PC*	UC*			
Randomised under incorrect stratification factor					
Switched circle after 1 st session attended					
Incorrect allocation received					
Other					

*PC: pregnancy circle, UC: usual care

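### The mean-imputation row of the missing-attendance check nearly reproduces the complete-case slope by construction, and no row tests low or zero attendance

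*SAP*

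**What the plan says.** SAP section 5.14 relates the number of circle sessions attended to the healthy-baby outcome. On the variable it says "The scale of this attendance variable is 0-8", and on the model "Dose will be used as a continuous variable assessed in a model fitted on intervention group participants only". It does not state the link function, covariates or random effects, or what happens when the session count is missing. The reference row, labelled as the original assumption in Table 15, is taken here to be complete case, from the general rule in section 5.5: "All main analyses will be performed on a complete case basis".

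Section 5.16.6 then varies the missing-data assumption in two steps. First, "we will consider that women attended all sessions where there is a missing value". Second, "we will impute the median and then mean value for women where the number of session(s) is missing". Table 15 in section 8.4, captioned "Results of dose-response relationship between primary outcome and number of antenatal care sessions attended with different missing data assumptions", sets out four rows: original, mean, median and attendance imputation. The main result is in Table 10. No row assumes low or zero attendance. The multiple imputation in section 5.16.1 covers the primary outcome, the stratification variables and four named baseline characteristics; session count is not among them.

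**The concern.** A sensitivity analysis for missing data is useful only if its answer can differ from the main one when the main one is wrong. Single imputation at the mean puts every woman with a missing count at the centre of the dose scale, where she carries almost no information about the slope. Agreement between that row and Table 10 would then be a property of the method and not evidence about the women with missing counts. The row would also carry a larger number analysed, which can look like added support.

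Outcome-related missingness is plausible here. Section 8.2 notes that women who deliver early can miss up to four sessions, and under section 3.2 birth before 37 weeks fails the composite. Section 3.1 lists antenatal attendance as collected at the 35-week follow-up and from birth records. The note to section 3.3 says that women with a pregnancy loss are not sent that questionnaire and that those delivering before 35 weeks are unlikely to complete it. The SAP does not say where the circle session count comes from, so this pattern is possible but not established.

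**Working it through.** The SAP gives no dose-response slope and no missing-attendance rate, so there is no figure of its own to reproduce on this point.

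**Inputs from the SAP.** Dose 0 to 8, entered linearly, intervention arm only (5.14). Arm size about 949: 395 + 271 intervention women from the dose table in 8.3, plus half of the 566 later recruits in 4.1.2, so 395 + 271 + 283 = 949.

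**Assumptions, not in the SAP.** Healthy-baby rate 73%; odds ratio per session 1.05, 1.10 or 1.20; four attendance shapes (symmetric, left-skewed, bimodal, right-skewed); 5% to 40% of counts missing; healthy-baby rate in women with missing counts 0 to 18 points away from the rest.

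**Step 1, linear model.** The slope is Σ(x − x̄)(y − ȳ) / Σ(x − x̄)². Adding women at x = x̄ leaves x̄ unchanged. Each contributes zero to the denominator and, because Σ(x − x̄)ȳ = 0, zero to the numerator. The slope is therefore identical. Numerically it was 0.043622 in both analyses.

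**Step 2, logistic model.** The added women mainly move the intercept; the slope moves only indirectly. Largest shift from the complete-case slope over all shapes and odds ratios:

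| Missing | Outcome difference | Mean row | Median row | All sessions attended |
|---|---|---|---|---|
| 10% | 0 | 0.02 SE | 0.16 SE (3%) | 1.87 SE |
| 10% | 10 points | 0.19 SE (3%) | 0.50 SE (24%) | 2.88 SE |
| 10% | 18 points | 0.31 SE (6%) | 0.75 SE (41%) | 3.61 SE |
| 20% | 0 | 0.05 SE (1%) | 0.29 SE (5%) | 2.62 SE |
| 20% | 10 points | 0.33 SE (6%) | 0.88 SE (47%) | 3.94 SE |
| 20% | 18 points | 0.64 SE (13%) | 1.30 SE (83%) | 4.87 SE |
| 40% | 18 points | 1.33 SE (31%) | 2.21 SE (169%) | 5.40 SE |

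**Step 3, one case in full.** Left-skewed attendance (mean 5.07, median 6), odds ratio 1.10, 20% missing, healthy-baby rate 55% in women with missing counts:

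- complete case 0.0953
- mean 0.0891 (−7%)
- median 0.0626 (−34%)
- all attended 0.0091 (−90%)

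The number analysed rises from 0.8 × 949 = 759 to 949.

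**Step 4, adjustment and clustering.** Data were simulated with site and circle effects and analysed with adjustment for English level and site. The slope used was 0.0953, with 21% missing depending on outcome only (healthy-baby rate 55% in women with missing counts, 75% in the rest). Average slopes were complete case 0.090, mean 0.082, median 0.052, all attended −0.009. Here the complete-case slope is close to the truth, and the median row moves away from it.

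**Step 5, when the complete-case slope is biased.** With 11–18% missing under assumed patterns, the mean row stayed within about 0.2 SE of the complete-case slope. For example: full data 0.228, complete case 0.179, mean 0.176. The mean row repeats the bias.

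**Step 6, does the remedy work?**

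- Multiple imputation with gestation and sessions held as predictors recovered 0.227 of 0.228 when missingness followed early delivery, but only 0.160 of 0.227 when it depended on the unrecorded attendance itself.
- In a separate set of simulations (946 women, true slope 0.15, 8–9% missing, mostly low attenders with an unhealthy outcome), imputation on outcome alone gave 0.053 against a complete-case 0.052 with skewed attendance, and 0.019 against 0.018 with symmetric attendance. It added nothing.
- In those two cases the all-attended row gave −0.046 and −0.184, and a none-attended row 0.158 and 0.212. The two bounds together bracketed 0.15.

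**The case against.** A reader might infer that both the mean and the median rows are redundant by construction, so that Table 15 as a whole would falsely confirm a biased slope. The documents do not support that, for three reasons.

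- **The median row is not automatic.** On a 0-to-8 count with late bookers, early deliveries and non-attenders, skew is plausible, and the median can then sit about a session from the mean. With outcome-related missingness the row moves by around one SE.
- **The table has an alarm.** The all-attended row moved by several SE in the patterns where the complete-case slope was badly wrong, and the SAP nowhere says that agreement between rows counts as confirmation.
- **Even the mean row is not fixed.** Exact equality needs an unadjusted linear model. The outcome is binary, section 5.14 leaves the model form open, and heavy, strongly outcome-related missingness shifts the mean row too.

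It can also be said that multiple imputation assumes missing at random and so may agree with complete case just as automatically. That stands for imputation on the outcome alone. It does not stand when gestation and sessions held are included and missingness follows early delivery. It does mean that imputation is not sufficient by itself.

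All of this leaves the narrower point intact: one of the three alternatives can hardly differ from the reference at modest missingness, and none looks in the low-attendance direction.

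**Conclusion.** The point holds in a limited form. The mean row is nearly uninformative: exactly so in an unadjusted linear model, and within about a third of an SE in logistic regression at 10% missing across the patterns examined. It weakens as a criticism at 40% missing with an 18-point outcome difference, where the shift reaches 1.33 SE. The median row shares the defect only if the median is near the mean or missingness is unrelated to outcome. Otherwise it moves, but its movement has no clear meaning and can be away from the truth. The all-attended row is a real stress test in the high-attendance direction only.

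These sizes rest on assumed attendance shapes, missing fractions and outcome differences. If few counts are missing, or if they are missing at random, little is lost. Importance is low: this is a sensitivity check on an exploratory comparison within one arm, without randomisation of dose, and it does not touch the primary result.

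**What to change.** Change step 2 of section 5.16.6, and the matching rows of Table 15:

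1. Replace the mean and median rows with multiple imputation of sessions attended. Predictors should include the primary outcome, gestation at birth, the number of sessions the circle actually held, circle or site, and baseline variables. Combine by Rubin's rules, as in 5.16.1.
2. Keep the all-sessions-attended row as the upper bound.
3. Add a row for no attendance, or a stated low attendance, as the lower bound. This is needed because the imputation assumes missing at random and recovered only part of the slope when missingness depended on the unrecorded count.

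The cost is a few lines of SAP text and modest extra programming on imputation methods already planned. No new data collection is implied if gestation and sessions held are already recorded.
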